6.1.5 Other Treatment Procedures

There are no other treatment procedures in this protocol.

6.1.6 Product Complaints

A product complaint is any written, electronic or oral communication that alleges deficiencies related to the identity, quality, durability, reliability, safety, effectiveness, or performance of a drug(s), combination product, or device(s) after it is released for distribution to market or clinic by either (1) Amgen or (2) distributors or partners for whom Amgen manufactures the material. This includes all components distributed with the drug, such as packaging drug containers, delivery systems, labeling, and inserts.

This includes any investigational or non-investigational product(s) provisioned and/or repackaged/modified by Amgen.

Any product complaint(s) associated with an investigational product(s) or non-investigational products supplied by Amgen are to be reported according to the instructions provided in the IPIM.

6.1.7 Excluded Treatments, Medical Devices, and/or Procedures During Study Period

The following medications and/or therapies should not be administered within the timeframes specified prior to enrollment or during the study (unless otherwise specified below):

- Allogenic stem cell transplant

- Autologous stem cell transplant
- Anti-tumor therapy (chemotherapy, antibody therapy, molecular targeted therapy, retinoid therapy, or investigational agent or procedures); concurrent use of bisphosphonates or denosumab for bone loss are permitted. In subjects with AML hydroxyurea is allowed to control blasts as described in Section [6.7.2](#).
- NOTE: Hydroxyurea is unapproved for AML in Japan.
- Treatment with medications known to cause QTc interval prolongation unless approved by the Amgen Medical Team
- Any live vaccine therapies used for the prevention of infectious disease
- Any major surgery or radiotherapy unless agreed upon by Amgen and investigator
- Over the counter medication(s) that was not reviewed and approved by the principal investigator and the Amgen medical monitor
- Herbal medicines (eg, St. John's wort) that were not reviewed and approved by the principal investigator and the Amgen medical monitor

The use of certain medications and illicit drugs within 5 half-lives or 28 days, whichever is shorter prior to the first dose of study drug and for the duration of the trial will not be allowed. If a prohibited medication is required for single use (such as for a procedure) while study drug is held, the Amgen medical monitor can approve such use.

The following medications or non-drug therapies are prohibited:

- Use of known strong inhibitors of CYP3A4/P-gp such as ketoconazole, itraconazole, HIV protease inhibitors, nefazodone, cyclosporine, erythromycin, clindamycin, tetracycline, and clarithromycin within the 14 days or 5 times the $t_{1/2}$ of the drug, or until the relevant biological effect has resolved (whichever is longer); or products containing grapefruit, Seville oranges, or St. John's wort within 7 days, prior to enrollment. Exception: use of azole antifungal therapies.
- Use of known CYP3A4 sensitive substrates with a narrow therapeutic window (such as pimozide, and sirolimus) within 5 half-lives of the drug or its major active metabolite, whichever is longer, following the last dose of the drug prior to receiving the first dose of AMG 176. Refer to prescribing information for concomitant medications.
- Use of known OATP1B1 and/or OATP1B3 substrates with a narrow therapeutic window within 5 half-lives of the drug or its major active metabolite, whichever is longer, following the last dose of the drug prior to enrollment. Refer to prescribing information for concomitant medications.
- Use of known BCRP substrates with a narrow therapeutic window within 5 half-lives of the drug or its major active metabolite, whichever is longer, following the last dose of the drug prior to enrollment. Refer to prescribing information for concomitant medications.

- Use of oral contraceptives (either combined or progesterone only), estrogenic vaginal ring/percutaneous contraceptive patches, or implants of levonorgestrel/Injectable progesterone for the purpose of pregnancy prevention is prohibited in this study as it is not known if there is the potential of inhibition/induction of enzymes that affect the metabolism of estrogens and/or progestins. However, oral contraceptives may be used for the treatment of menorrhagia or other abnormal menstrual bleeding at the discretion of the investigator.

If use of any other prior or concomitant medication or procedure is in question, please refer to prescribing information and/or consult with the Amgen medical monitor.

There are no prohibited therapies and procedures during the 30-day safety follow-up or the long-term follow-up.

6.1.8 Concomitant Medications with Itraconazole (Part 3d only)

Itraconazole has the potential to interact with many concomitant drugs. Please refer to the current itraconazole US Prescribing Information (USPI) for additional information including:

- Medications which are contraindicated and prohibited during and after the last dose of itraconazole administration
- Medications which are not recommended during and after the last dose of itraconazole administration
- The following medications are contraindicated with itraconazole and should not be administered during concomitant administration with itraconazole: cisapride, oral midazolam, nisoldipine, pimozide, quinidine, dofetilide, triazolam, levacetylmethadol (levomethadol), and ergot alkaloids such as dihydroergotamine, ergometrine (ergonovine), ergotamine, and methylergometrine (methylergonovine). This is not an exhaustive list; please refer to itraconazole USPI for additional details.

6.2 Dose Modification

6.2.1 Dose-cohort Study Escalation/De-escalation and Stopping Rules

Dose Level Determination

The DLRT will be responsible for dosing recommendations, which may include escalation to the next nominal or intermediate dose, de-escalation to a lower nominal or intermediate dose; modifications of the ramp-up dosing, alternative dose frequencies, continuation, delay or termination of dosing; or repetition or expansion of a cohort; or determination of recommended dose. Refer to Section 11.3 for additional details regarding the DLRT.

6.2.1.1 Dose-Limiting Toxicity Evaluation Period

The minimum DLT evaluation period is defined as 4 weeks of treatment in cycle 1.

The DLT evaluation period may also be extended to assess events starting within the evaluation period in case the DLT definition is time dependent (neutropenia or thrombocytopenia, see below).

Subjects are considered DLT-evaluable if they experienced a DLT during the DLT evaluation period or if they received 75% of the planned doses of AMG 176 (and 100% of the planned doses of azacitidine in Part 4) and completed the DLT evaluation period.

Subjects who did not complete 75% of the planned doses of AMG 176 (and 100% of the planned doses of azacitidine in Part 4) or discontinue from the study prior to completing the DLT evaluation period for reasons other than a DLT will be considered non DLT-evaluable for dose escalation decisions and MTD/MTCD determination and will be replaced by an additional subject at that same dose level. Subjects who receive supportive care during the DLT evaluation period that confounds the evaluation of DLTs (not including supportive care described in Section 6.2.1.2 as part of the DLT definition) may be considered non-evaluable for dose escalation decisions and MTD determination and replaced at the discretion of the Medical Monitor.

6.2.1.2 Definition of Dosage Limiting Toxicities

A DLT will be defined as any of the events described below occurring in a subject during the DLT evaluation period and regarded by the investigators and/or Amgen medical monitor to be related to AMG 176.

Any adverse event occurring outside the DLT evaluation period that is determined by the investigator to be possibly related to the investigational product, which is seen more frequently or is more severe than expected or is persistent despite appropriate management, can be determined to be a DLT upon unanimous decision by the DLRT after review of the adverse event and all available safety data. The grading of adverse events will be based on the guidelines provided in the CTCAE version 4.0 (available online at <http://evs.nci.nih.gov/ftp1/CTCAE/About.html>). For troponin elevation, refer to Section 6.2.1.2.2 for CTCAE grading interpretation. Determination of the severity of adverse events will be consistent with CTCAE version 4.0. The relationship of an adverse event to investigational product will be determined by the investigator. An event should be considered related to treatment if, in the investigator's medical judgment, there is a reasonable possibility that the event may have been caused by AMG 176.

6.2.1.2.1 Dose-Limiting Toxicities

A DLT is defined as a grade 3 or higher non-hematological or a grade 4 hematologic adverse event that occurs during the DLT observation period (day 1 through day 28 after the administration of the first dose of AMG 176) in Parts 1 BIW and QW Dose Escalation unless clearly attributable to causes other than AMG 176 treatment.

If a DLT of TLS is observed during the ramp-up period, it will be attributed to the ramp-up period and a modification may be made to the ramp-up period regimen for subsequent groups. Any other DLTs observed during the ramp-up and/or designated group dosing period may require a modification of the designated cohort dose (and/or ramp-up period regimen, if appropriate) as directed per the Dose Escalation Guidelines.

Available study data, including data collected after the initial DLT-observation period along with demographics, investigational product administration, medical history, concomitant medications, adverse events, ECG, vital signs, laboratory results, and PK/PD information will be reviewed. In addition to DLTs, all \geq grade 3 toxicities not meeting DLT criteria will be reviewed and may be considered in DLRT decisions.

Modeling of available potential safety risk data (eg, for thrombocytopenia) to predict safety risk for dose escalation decisions may also be considered.

Table 6-1. DLT Criteria

	Multiple Myeloma Subjects	Acute Myeloid Leukemia Subjects	All Subjects
DLT Criteria	
Non-hematologic adverse events:
grade 3 nausea, vomiting, or diarrhea persisting more than 3 days despite optimal medical support. \geq grade 4 nausea, vomiting, or diarrhea of any duration would be considered as a DLTgrade 3 fatigue lasting > 7 days\geq grade 3 acute kidney injury (creatinine > 3 \times baseline or > 4.0 mg/dL) lasting > 3 daysany treatment-related death	
Non-hematologic adverse events:
\geq grade 3 non-hematologic adverse event that is not clearly resulting from the underlying leukemiarecurrence within the DLT window of any adverse events listed under the non-hematologic adverse event exception (not including nausea and vomiting)any grade 2 non-hematologic adverse event lasting > 7 days that causes significant symptoms, dangerous medical repercussions, or warranting treatment interruption or dose reduction\geq grade 3 nausea, vomiting or diarrhea persisting more than 3 days despite optimal medical support\geq grade 3 fatigue persisting > 7 daysany other \geq grade 3 adverse eventfailure to recover from AMG 176 related toxicities to grade \leq 1 or baseline severity after delaying next cycle up to 14 days	
any clinical TLS per Cairo-Bishop criteria (see Section 11.8.3) despite the use of prophylaxisDILI meeting Hy's Law criteria (ie, AST or ALT \geq 3 \times ULN and serum bilirubin > 2 \times ULN measured on the same day, without signs of cholestasis and in absence of any other explanation for the DILI). See Section 6.2.3 for hepatotoxicity managementgrade 3 elevation of troponin-I (see grading criteria in Section 6.2.1.2.2)^a

Page 1 of 3

Footnotes defined on last page of the table

Table 6-1. DLT Criteria (continued)

	Multiple Myeloma Subjects	Acute Myeloid Leukemia Subjects	All Subjects
DLT Criteria	
hematologic adverse events:
grade 3 or 4 neutropenia with fever > 38.5°Cgrade 4 neutropenia lasting > 7 daysgrade 3 thrombocytopenia with ≥ grade 2 hemorrhagegrade 4 thrombocytopenia lasting > 7 daysgrade 3 anemia with symptoms or requiring intervention (eg, transfusion)grade 4 anemia≥ grade 4 hematologic adverse eventsany grade 5 adverse event that is not clearly due to disease progression	
hematological adverse events:
grade 4 neutropenia or thrombocytopenia lasting ≥ 42 days from start of cycle in absence of evidence of active AMLany treatment-related death	
Symptoms of clinically significant cardiac dysfunction, ECG changes, or diagnostic evidence of decreased cardiac function or cardiac injury irrespective of any cardiac troponin-I level (central or locally obtained)

Page 2 of 3

Footnotes defined on last page of the table

Table 6-1. DLT Criteria (continued)

	Multiple Myeloma Subjects	Acute Myeloid Leukemia Subjects	All Subjects
Exceptions	
The following adverse events are not DLTs unless the specific criteria above are met:
 
• Fatigue• Nausea• Diarrhea• Vomiting• Neutropenia• anemia• thrombocytopenia• lymphopenia• increased serum creatinine or electrolyte abnormalities 
Non-hematological adverse events:
 
• grade 3 or 4 elevation of serum lipase in absence of clinical pancreatitis that last < 72 hours	
• Infections and most hematologic adverse events• Non-hematologic adverse events:
- grade 3 weight gain or loss- grade 3 diarrhea despite optimal anti-diarrheal therapy that resolves to ≤ grade 2 within < 72 hours with or without clinical intervention- grade 3 or 4 isolated electrolyte abnormalities that is not clinically significant and resolves to ≤ grade 2 within 72 hours with or without clinical intervention- grade 3 nausea and vomiting that does not require tube feeding, total parenteral nutrition, or prolonged hospitalization and resolves to ≤ grade 2 within < 72 hours with or without clinical intervention- grade 3 or 4 serum lipase without clinical signs or symptoms of pancreatitis that returns to baseline within 72 hours of interrupting study drug- infection grade 3 (with concurrent neutropenia grade 3 or 4) that resolves to ≤ grade 2 within 7 days with or without clinical intervention- grade 3 fatigue or asthenia- grade 3 constipation that resolves to ≤ grade 2 within 7 days with or without clinical intervention	N/A

Page 3 of 3

AML = acute myeloid leukemia; ALT = alanine aminotransferase; AST = aspartate aminotransferase; DILI = drug-induced liver injury; DLT = dose-limiting toxicity; ECG = electrocardiogram; N/A = not applicable; TLS = tumor lysis syndrome; ULN = upper limit of normal; URL = upper reference limit

^a Further treatment with AMG 176 may be considered for grade 1 elevations of troponin-I (ie, isolated elevation of troponin > 99th percentile URL of 0.04 ng/mL for females and 0.059 ng/mL for males) after a cardiology evaluation is completed and results are discussed with the Amgen medical monitor.

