In this study, Part 1 and Part 2 were initially designed to investigate AMG 176 as monotherapy and combinational therapy in subjects with multiple myeloma (MM). As of December 2019, 48 subjects were enrolled in Part 1 where clinical responses were observed at dose levels $> 240 \text{ mg/m}^2$. However, AMG 176 associated elevations of troponin were observed at dose levels of 360 and 480 mg/m^2 in MM subjects. In contrast, clinical responses in AML were observed at the lower dose levels, indicating that AML may be more susceptible to MCL1 inhibition and can be treated with lower doses compared to subjects with MM. The combination of these observations led to further development in AML and a pause in MM development for now. Part 1 will remain closed to enrollment and Part 2 was removed from the protocol during Amendment 10. To avoid the potential for troponin elevations, only doses $\leq 240 \text{ mg/m}^2$ will be further investigated. Additionally, preclinical data demonstrates that MCL1 inhibition is more efficacious in combination with other antileukemic therapies. Consequently, combinational therapy will be prioritized in this study (Parts 4 and 5) to optimize the clinical benefit to subjects, and monotherapy dose escalation will be performed only to inform the combinational study, and not to confirm the likely monotherapy maximum tolerated dose (MTD) of 240 mg/m^2 . As of November 2022, 33 subjects have been enrolled in monotherapy (Part 3b: 11 subjects) and combination therapy (Part 4: 22 subjects) cohorts at dose levels of $\leq 240 \text{ mg/m}^2$; no concerning safety events (including elevations of troponin) and no Dose-Limiting Toxicities (DLTs) were observed.

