
Evaluate the safety and tolerability of AMG 176 in combination with azacitidine in subjects with relapsed or refractory AML and in Part 4 only, determine the maximum tolerated combination dose (MTCD) of AMG 176 in combination with azacitidine	
Incidence of DLTs (Part 4 only), treatment-related, treatment-emergent adverse events and clinically significant changes in vital signs, ECGs, and clinical laboratory tests

Evaluate the PK of AMG 176 and azacitidine when administered in combination	
PK parameters for AMG 176 and azacitidine including, but not limited to, C_{max}, AUC, CL, and $t_{1/2}$

Secondary
	

Multiple Myeloma Part 1a (BIW)
	

Demonstrate inactivation of myeloid cell leukemia sequence 1 (MCL1) by the increase of active B-cell lymphoma/leukemia 2 associated X protein (BAX) and caspase 3 in circulating monocytes and/or the decrease of circulating monocytes in AMG 176 BIW treated subjects	
BAX and caspase 3 expression in circulating monocytes and/or circulating monocyte counts

Evaluate preliminary efficacy of AMG 176 BIW when given as monotherapy in relapsed or refractory MM	
Overall response (OR) according to International Myeloma Working Group uniform response criteria (IMWG-URC) for MM subjects, progression-free survival (PFS), time to response, and duration of response (DOR)

Multiple Myeloma Part 1b (QW)
	

Demonstrate inactivation of MCL1 by the increase of active BAX and caspase 3 in circulating monocytes and /or the decrease of circulating monocytes in AMG 176 QW treated subjects	
BAX and caspase 3 expression in circulating monocytes and /or circulating monocyte counts

Evaluate preliminary efficacy of AMG 176 QW when given as monotherapy in relapsed or refractory MM	
Overall response according to IMWG-URC for MM subjects, PFS, time to response, and DOR

[figure not shown]
Acute Myeloid Leukemia Part 3a (BIW), Part 3b (QW), and Part 3c (QW)	

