
For AML Part 3b and Part 4, each dose cohort will initially enroll 3-4 subjects and up to 10 subjects per cohort may be enrolled. After reviewing all available safety and tolerability data, dose level decisions (eg, escalation/de-escalation/expansion) will be made by the DLRT using a modified Toxicity Probability Interval (mTPI) model (Ji et al, 2010) based on all subjects that have been enrolled at current dose. Dose escalation is considered to be complete if one of the following rules is met:

- The highest planned dose level is evaluated, MTD/MTCD has not been defined and no DLTs occur at any dose level. In this case the maximum administrated dose (MAD) may be used for phase 2.
- An MTD/MTCD is identified.

Guidelines for dose level decisions can be found in [Table 4-2](#). Details regarding the mTPI model and dose finding are described in Section [11.16](#). Please note one exception to the guidelines provided in [Table 4-2](#), a single grade 3 treatment-related troponin elevation will result in dose de-escalation regardless of number of subjects treated at current dose.

Table 4-2. Guidelines for Dose-level Decisions for Part 3b and Part 4

No. of DLT-evaluable ^a subjects treated at current dose	Number of DLTs		
	Escalate	Stay at current dose	De-escalate ^b
3	0	1	≥ 2
6	0-1	-	≥ 2
9	0-1	2	≥ 3
10 ^c	0-1	2-3	≥ 4

DLT = dose-limiting toxicity

^a A subject is considered DLT-evaluable if he/she experienced a DLT during the DLT evaluation period or if he/she received 75% of the planned doses of AMG 176 and completed the DLT evaluation period.

^b De-escalate guideline applies only when current dose level and enrollment is allowed to a lower dose level.

^c The maximum number of evaluable subjects at one dose level is 10.

The MTD/MTCD is defined as the highest dose with a probability of DLT lower than or close to a targeted toxicity probability of 0.2.

For the first dose level and at each new higher dose level, the first enrolled subject will be treated, and then after a period of 72 hours, subsequent subjects will be treated, provided that there are no significant toxicities relating to the treatment of the first subject.

In addition to safety, efficacy of complete remission per ELN in Part 4 will be evaluated. At MTCD or optimal biological dose (OBD), 1 complete remission out of 6 subjects, or 2 complete remissions out of 10 subjects are expected.

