Gastrointestinal disorders	Abdominal distension, abdominal pain, constipation, diarrhea, gingival pain, nausea
General disorders and administration site reaction	Fatigue, pyrexia, malaise, pain, chest pain
Infections and infestations	Infection ^a , sepsis
Investigations	Alanine aminotransferase increased, aspartate aminotransferase increased, alkaline phosphatase increased, white blood cell decreased, hemoglobin decreased, platelet count decreased
Metabolism and nutrition disorders	Decreased appetite, hypokalemia, hyponatremia, hypocalcemia, hyperuricemia
Musculoskeletal and connective tissue disorders	Skeletal pain, muscular pain, arthralgia, generalized muscle weakness, neck pain
Nervous system disorders	Cranial nerve disorder, dizziness, headache, lethargy, meningismus, syncope
Respiratory, thoracic, and mediastinal disorders	Cough, dyspnea, epistaxis, pleuritic pain
Other	Hemorrhage ^b

^a Represents preferred terms under Infections and infestations SOC

^b Represents haemorrhage HLGT preferred terms contained within multiple SOCs. Coded: MedDRA 17.0

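### Table 6-1, AML column: the exception for grade 3 fatigue has no time limit and, read literally, cancels the DLT criterion for fatigue lasting more than 7 days; the practical effect is small

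*Protocol*

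**What the plan says.** Protocol Section 6.2.1.2.1, Table 6-1, sets criteria and exceptions in separate columns for multiple myeloma (MM) and AML.

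- **AML criteria.** Fatigue of at least grade 3 that persists beyond 7 days is a DLT. So is a grade 2 non-hematologic event of more than 7 days with significant symptoms, dangerous consequences, or a need to interrupt or reduce dosing. Two broad lines also make DLTs of grade 3 or higher events in general.
- **AML exceptions.** The list includes "grade 3 fatigue or asthenia", with no duration or resolution condition.
- **MM exceptions.** The list opens with a ranking sentence: "The following adverse events are not DLTs unless the specific criteria above are met". The AML list has no such sentence.

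Section 6.2.1.2 requires that a DLT be "regarded by the investigators and/or Amgen medical monitor to be related to AMG 176". It does not rank criteria against exceptions. The general DLT sentence in Section 6.2.1.2.1 is confined to Part 1, so it does not settle the AML case.

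**The concern.** Two lines of the same column give opposite answers for one event. DLT incidence is a primary endpoint in Part 4 and is the count that enters the table headed "Guidelines for Dose-level Decisions for Part 3b and Part 4" (Table 4-2). The same definition has three other uses:

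- **Evaluability (Section 6.2.1.1).** A subject with a DLT is evaluable whatever was received. Without one, the subject needs 75% of planned AMG 176 doses (and all azacitidine in Part 4), or is replaced. On weekly dosing, two missed doses out of four is 50%, so prolonged fatigue that interrupts treatment could either count as a DLT or drop out of the denominator.
- **Withholding (Section 6.2.2.1).** A suspected DLT stops dosing, also outside the observation period.
- **Permanent discontinuation (Section 6.2.2.1).** Meeting DLT criteria at any time ends treatment, except for subjects who are or may be responding.

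**Working it through.** **Step 1. Compare the AML lines.** Take one continuous grade 3 fatigue episode of 8 days, judged related.

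| Line | Result |
|---|---|
| 7-day fatigue criterion | DLT |
| Fatigue/asthenia exception, as written | Not a DLT |
| Recurrence of an excepted event | Does not apply: one episode |
| Failure to recover after a delay of up to 14 days | Does not apply if recovered in time |
| Grade 2 event beyond 7 days with consequences | Does not apply to the grade 3 days |

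The neighbouring AML exceptions for diarrhea, electrolytes, nausea and vomiting, lipase, infection and constipation all carry time limits. Fatigue has a duration-based criterion but no matching limit in its exception.

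**Step 2. Test the literal reading.** If the exception wins, grade 2 fatigue beyond 7 days that leads to dose interruption is a DLT, because only grade 3 fatigue is excepted. Grade 3 fatigue of the same length is not. The milder event would count and the more severe one would not.

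**Step 3. Where could one event change a dose decision?** Inputs are from Appendix 16: prior Beta(0.5, 0.5), intervals (0, 0.15), [0.15, 0.25], (0.25, 1), and closure of a dose if P(p > 0.2) exceeds 0.80. With x DLTs in n subjects the posterior is Beta(0.5 + x, 0.5 + n − x). The unit probability mass (UPM) is the posterior probability of an interval divided by its width.

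| x/n | UPM under / proper / over | P(p > 0.2) | Table 4-2 |
|---|---|---|---|
| 1/6 | 2.66 / 2.53 / 0.46 | 0.465 | Escalate |
| 2/6 | 0.73 / 1.88 / 0.94 | 0.804 | De-escalate |

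At n = 6 one extra event moves the decision from escalate to de-escalate, and only if there is exactly one other DLT. The UPM at 2/6 favours staying; the size of the step comes from the 80% rule and from the absence of a stay cell at n = 6. At n = 3, 9 and 10 one event moves the Table 4-2 decision by at most one step.

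**Step 4. How likely is that pattern?** The documents give no rate for the disputed event (q), so 1% to 5% per subject is assumed. For other DLTs (p), Section 2.1 reports of 33 Part 3b and Part 4 subjects that "no Dose-Limiting Toxicities (DLTs) were observed". If all 33 were evaluable and doses are pooled, the one-sided 95% upper bound is 1 − 0.05^(1/33) = 0.087. The lower value of 2% is assumed. Six subjects with exactly one disputed event, exactly one other DLT and four with neither have probability 6 × 5 × q × p × (1 − q − p)^4.

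| q | p | Probability |
|---|---|---|
| 0.01 | 0.02 | 30 × 0.0002 × 0.97^4 = 0.005 |
| 0.01 | 0.087 | 30 × 0.00087 × 0.903^4 = 0.017 |
| 0.05 | 0.02 | 30 × 0.001 × 0.93^4 = 0.022 |
| 0.05 | 0.087 | 30 × 0.00435 × 0.863^4 = 0.072 |

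A value of p = 0.20 with q = 0.05 would give 0.095, but at that p the chance of no DLT in 33 subjects is 0.8^33 = 0.0006. If disputed events were being counted as DLTs, the 0.087 bound applies to p + q. With q = 0.05 and p = 0.037 the result is 30 × 0.00185 × 0.913^4 = 0.039.

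**The case against.** The strongest reply is that only one reading makes sense. The exception carves short-lived fatigue out of the broad grade 3 lines, and the dedicated 7-day criterion governs longer episodes. Step 2 supports this, and it stands as the likely intention. It does not show that the text is right: the AML exceptions have to override the broad grade 3 lines to do anything at all, so a reader may reasonably apply them to every line.

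The position of the ranking sentence is read from an extracted table, so whether it was laid out for MM alone deserves some caution. The AML cell nevertheless has no such sentence of its own.

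Attribution will settle some cases first, since Table 11-3 lists fatigue among expected AML events ("Fatigue, pyrexia, malaise, pain, chest pain"). The dose-level review team also sees these events: grade 3 or higher "toxicities not meeting DLT criteria will be reviewed and may be considered in DLRT decisions". Both points stand. Neither decides whether a related event is counted as a DLT.

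A reader might infer that prolonged grade 3 fatigue is excluded from AML DLTs altogether, or that a dose was escalated or closed wrongly. The documents support neither. Recurrent episodes, episodes without timely recovery, and episodes that also spend more than 7 days at grade 2 with the listed consequences remain DLTs. Table 4-2 is a guideline, and no affected cohort is described.

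**Conclusion.** The AML column is wrong as written, with a small effect. The conflict is confined to a single continuous grade 3 fatigue episode of more than 7 days, judged related to AMG 176, that recovers in time and meets no other criterion. Its consequence is inconsistent classification, not a demonstrated error in any dose decision.

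The range of about 0.005 to 0.07 for a reversal in a cohort of six is illustrative. It rests on the assumed event rate of 1% to 5%, an other-DLT rate between 2% and the 8.7% bound, independence between subjects, all 33 subjects being evaluable, and pooling over doses. It would be a mistake to charge the full escalate-to-closure step to this wording, because any borderline event would have the same effect at n = 6.

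Reach is limited further: Part 3b is closed, Part 5 has no DLT endpoint, and SAP Section 10 records early termination. DLT incidence is not among the analyses dropped there, and SAP Sections 9.6.1 and 9.6.2 still call for it, so one classification rule is still needed.

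**What to change.** In the AML exceptions of Table 6-1, extend "grade 3 fatigue or asthenia" with: *unless the criterion above for fatigue lasting more than 7 days is met*. Fatigue of up to 7 days stays exempt, longer fatigue is a DLT as already listed, and asthenia is left as it is. If the sponsor also wants asthenia beyond 7 days to count, the criterion itself should name it, because that would be a change of content. Copying the MM sentence into the AML cell is less safe: the AML criteria include broad grade 3 lines, and it would be unclear which of them are specific.

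Since the study has ended early, apply the same rule when classifying events for the DLT incidence or subject listing still to be reported, and state it in the report. The cost is one line in the table and one sentence in the report.
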